9.4.3 ANALYSIS OF THE SECONDARY ENDPOINT(S)

The safety measures of occurrence of Stroke/TIA, cerebral hemorrhage, or death will be analyzed as frequency within the 30-day post-procedure period. Analysis will be done in aggregate of the events combined and individually using a Kaplan-Meier survival estimation with a Logrank test. Adjustment for age, etiology of ischemia, and side of occlusion will be done using a Cox Model Regression. A two-sided type I error rate of 0.05 will be used.

Analysis of the Tertiary/exploratory Endpoint

Tertiary/exploratory endpoints will be analyzed individually. The presence/absence of lactate will be estimated by a proportion and evaluated using a Fisher's Exact Test. The change in sizes of amygdala and hippocampus in the ipsilateral side of COICA will be using a T-Test of the difference. Improved and/or normalization of MTT and/or PTT on CTP specifically in the ipsilateral MCA territory will be analyzed using a T-Test.

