1.2 SCHEMA

1.3 SCHEDULE OF ACTIVITIES (SOA)

The schedule below is provided as an example and should be modified as appropriate.

Procedures	Screening Day -30 to -1	Enrollment/Baselining Visit 1, Day 0 ^f	Study Visit 4 6 Months +/- 6 weeks	Final Study Visit 12 months +/- 6 weeks
Informed consent	X			
Demographics	X			
Medical history	X			
Randomization ^a	X			
Administer study intervention		X ^e		
Concomitant medication review	X		X	
Physical exam (including height and weight)	X	X	X	X
Vital signs	X	X	X	X
Height	X			
Weight	X			
Performance status	X			
Hematology	X			
Serum chemistry ^a	X			
Pregnancy test ^b	X			
Blood Test ^c		X		
EKG (as indicated)	X			
Adverse event review and evaluation	X		X	
CTP	X	X		
MRA or CTA	X			
Radiologic/Imaging assessment (MRI of the brain)	X		X	X
Cognitive testing	X		X	X
Complete Case Report Forms (CRFs)	X	X	X	X
Diagnostic angiogram	X ^d			X ^c
Medication check			X	X

a- Not applicable to 3rd study arm

b- Only if necessary, to confirm surgery eligibility

c- Surgical arm only

d- Only applicable if the subject has not had one in the past 6 months

e- Prior to surgical intervention eligibility will be confirmed by adjudicator(s)

f- Enrollment for surgical arm may be delayed due to OR schedule

- g- 6-month follow up visit timeframe is based on the date of randomization for non-surgical date of surgery for surgical arm
- h- 12-month follow up visit timeframe is based on same dates as 6-month visit

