9.3 POPULATIONS FOR ANALYSES

Data analysis will be performed based on Intention-to-Treat (ITT).

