9.4 STATISTICAL ANALYSES

9.4.1 GENERAL APPROACH

The analysis will be intention to treat.

- 1) Comparison of treatment groups of baseline variables
- 2) Comparison of primary endpoint
 - a. MoCA change
 - b. Cognitive battery summary score
- 3) Comparison of secondary endpoints
- 4) Exploratory analysis of associations of exploratory endpoints with cognitive change

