9.4.4 SAFETY ANALYSES

Event rates by treatment group will be reported with 95% confidence intervals. The distribution by severity will be compared. Kaplan-Meier time to event curves will be done for AEs and deaths. Logrank tests will be performed.

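### The between-arm safety comparison has no start date in the medical arm, two endpoint definitions on TIA, and, if read as a 30-day analysis, too few expected events for its adjusted Cox model

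*Combined protocol and SAP*

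**What the plan says.** Section 9.4.1 lists a comparison of secondary endpoints and states "The analysis will be intention to treat"; Section 9.3 says the same. The only secondary endpoint is safety. Section 9.4.3 says that the events "will be analyzed as frequency within the 30-day post-procedure period". It continues: "Analysis will be done in aggregate of the events combined and individually using a Kaplan-Meier survival estimation with a Logrank test". It then adds: "Adjustment for age, etiology of ischemia, and side of occlusion will be done using a Cox Model Regression". Neither of these last two sentences repeats a window.

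Section 9.4.4 adds event rates by treatment group with 95% confidence intervals, and "Kaplan-Meier time to event curves will be done for AEs and deaths", again with no window or time origin.

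The Schedule of Activities (1.3) puts randomisation in the screening column, Day -30 to -1. Footnote f says "Enrollment for surgical arm may be delayed due to OR schedule". Footnote g is the only text that gives the two arms a time origin: "6-month follow up visit timeframe is based on the date of randomization for non-surgical date of surgery for surgical arm".

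The endpoint is stroke, cerebral hemorrhage or death in Sections 1.1, 3 and 4.1. In Sections 9.1 and 9.4.3 it is stroke/TIA, cerebral hemorrhage or death.

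**The concern.** A survival comparison needs a day 0 for every randomised patient. Here the clock starts at an event that only one arm undergoes. The analyst would have to choose the medical arm's day 0 after the fact, and the two windows need not start at the same point after randomisation. Surgical-arm events between randomisation and procedure fall outside the window, whereas medical-arm events soon after randomisation may fall inside it. Patients randomised to surgery and never treated, whom Section 7.2 foresees, have no window at all, which does not sit with intention to treat.

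The endpoint mismatch matters because Section 5.1 lists continued TIA symptoms despite medical management as an entry criterion, so including TIA could change the count materially. A smaller point of the same kind is that the outcome definition of stroke in Section 2.3.3 refers to deficits absent before the intervention, which does not plainly cover the medical arm.

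Finally, an adjusted Cox model on a handful of events may have no finite treatment estimate, and a non-significant logrank test on so few events could be misread as reassurance. Section 2.1 says that the data from this trial feed a go/no-go decision on phase 3.

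**Working it through.** **The plan's own figure.** Section 9.2 sizes the trial on MoCA only: difference 2, SD 2, two-sided 0.05, 80% power. A two-sample t-test needs 16.7, so 17 per arm, 34 in total. With 10% dropout, 34/0.9 = 37.8, so 38, or 19 per arm. This reproduces. No event rate, event count or power is given for safety, so the rest uses proxies.

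**Inputs.**
- Medical-arm stroke: 7 to 10% per year (2.1). A constant hazard is assumed.
- Procedural complications of any kind: 5.4% (literature review, 2.2) and 18.75%, 6/32, in the pilot over types A to D (2.2). Pilot types A and B had 0/16. Section 5.1 admits only A and B, although 9.2 still mentions C.
- Cox parameters: arm, age, etiology and side, so four if etiology takes one parameter. Section 5.1 requires atherosclerotic occlusion, so etiology may not vary, which leaves three. The plan does not define the term.

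**30-day window, TIA not counted.** 30-day risk = 1 − (1 − annual risk)^(30/365.25): 0.00594 at 7% and 0.00862 at 10%.
- Low: 19 × 0.00594 + 19 × 0.054 = 0.11 + 1.03 = 1.14 events.
- High: 19 × 0.00862 + 19 × 0.1875 = 0.16 + 3.56 = 3.73 events.
- Per parameter: 0.28 to 0.93 with four, 0.38 to 1.24 with three.

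The chance that at least one arm is empty is a + b − ab, where a and b are (1 − p)^19 in each arm.
- Low: 0.893 + 0.348 − 0.311 = 0.930.
- High: 0.848 + 0.019 − 0.016 = 0.851.

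The surgical inputs are generous, because they count every complication. Taking 0/16 at face value leaves only the medical arm's 0.11 to 0.16 events. However, the exact upper 95% limit for 0/16 is 1 − 0.025^(1/16) = 20.6%, so 18.75% is not ruled out.

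**30-day window, TIA counted.** The documents give no separate TIA rate. The nearest figure is in 2.2: TIA or stroke more than 30 days after the procedure in 4/10 failed revascularisations. Treating that as 40% per year in the medical arm is an assumption; the 30-day risk is then 0.0411, or 0.78 events. The upper surgical rate here is the 20% DSMB threshold.
- With 5.4%: 0.78 + 1.03 = 1.81. With 20%: 0.78 + 3.80 = 4.58.
- Per parameter: 0.45 to 1.15 with four, 0.60 to 1.53 with three.
- Chance of an empty arm: 64% and 46%.

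As a further assumption, adding a 10% 30-day TIA risk to both arms at the high rates gives 19 × 0.1086 + 19 × 0.2875 = 2.06 + 5.46 = 7.53 events. That is 1.9 per parameter with four and 2.5 with three.

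**12-month window.**
- Stroke rates, low: 19 × 0.07 + 19 × 0.054 = 2.36. High: 19 × 0.10 + 19 × (1 − 0.8125 × 0.90) = 7.01. Per parameter: 0.6 to 1.8 with four, 0.8 to 2.3 with three.
- 40% proxy, low: 7.6 + 1.03 = 8.63. High: 7.6 + 19 × (1 − 0.8 × 0.6) = 17.48. Per parameter: 2.2 to 4.4 with four, 2.9 to 5.8 with three.

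**Events before the procedure.** The delay is not stated. If it were 30 days, 0.11 to 0.16 surgical-arm strokes would be left out, or 0.78 events at the 40% proxy.

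**What a result would look like.** A 3/19 v 0/19 split is a risk difference of 15.8 points, with a Newcombe 95% interval of −3.9 to 37.6. Such a result would not demonstrate safety.

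**The case against.** The best reply is that the 30-day limit belongs only to the word frequency, and that Kaplan-Meier, logrank and Cox are meant to run over full follow-up. The text allows this, and Sections 1.1, 3 and 4.1 give the endpoint no window. On that reading the event count is higher. What stands is that the plan does not say which reading applies, and that on either reading the medical arm's time zero is missing.

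A second reply is that Section 9.4.4 already gives group rates with 95% intervals and unwindowed curves. That is a real mitigation. It may also capture events before the procedure. It gives no time origin, no definition of the secondary endpoint, and no interval for the difference between arms.

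A third is that footnote g supplies a convention. It covers visit timing only, and it starts the arms at different points, which is the problem.

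A reader might also infer that there must always be fewer than two events per Cox parameter. The documents do not support that bound. It holds at the documented 30-day rates, but it depends on an arbitrary cap on the TIA rate, on counting etiology as a parameter, and on the 30-day reading. Nor do they support a claim that many surgical-arm events would be lost before the procedure. The screening column does not establish a 30-day gap, and the expected number is below one even if there is one, although 0.78 would be 17 to 43% of the 1.8 to 4.6 events in the 40% scenario.

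**Conclusion.** The concern holds in three parts. First, the comparison is undefined as written: there is no time zero for the medical arm or for untreated surgical-arm patients, and the window for the time-to-event analyses is unclear. Second, current sections disagree on whether TIA counts. These two parts follow from the text and need no assumption.

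Third, the adjusted Cox model is not supportable. On the 30-day reading, the documented rates give about 1.1 to 3.7 events and an 85 to 93% chance of no finite treatment hazard ratio; with the TIA proxy the figures are 1.8 to 4.6 events and 46 to 64%. Higher TIA rates or 12 months of follow-up can exceed two events per parameter, up to about 4.4 with four parameters or 5.8 with three, which is still too few. The component-by-component analyses would have fewer events again. This part rests on 19 per arm, a constant hazard, and all-complication rates standing in for endpoint events. No inflation of type I error is claimed. The point should be fixed, but it does not touch the primary analysis.

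**What to change.** - In 9.4.3, use randomisation as time zero for all randomised patients, with one stated window common to both arms, and say that it governs the Kaplan-Meier and logrank analyses.
- Use one endpoint definition in 1.1, 3, 4.1, 9.1 and 9.4.3, and report TIA separately as well. Word the outcome definition of stroke in 2.3.3 so that it applies to both arms.
- Add the between-arm risk difference with a 95% confidence interval to the group rates already planned in 9.4.4. The logrank test may stay.
- If the window is 12 months, take the difference from Kaplan-Meier estimates with a stated censoring rule. The final visit may fall six weeks early and up to 10% dropout is expected, so some patients will not reach the end of the window. Add adverse event review at the existing 12-month visit, where the Schedule of Activities has no tick for it.
- Report the 30-day post-procedure rate descriptively in treated surgical patients, with an exact confidence interval.
- Drop the adjusted Cox model or label it exploratory.

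The cost is protocol and SAP wording, plus one schedule entry if the window is 12 months; no added patients. The adjusted hazard ratio is lost or becomes exploratory. A longer window mixes procedural harm with later events, which is why the 30-day surgical rate should be kept alongside.

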9.4.4 SAFETY ANALYSES

Event rates by treatment group will be reported with 95% confidence intervals. The distribution by severity will be compared. Kaplan-Meier time to event curves will be done for AEs and deaths. Logrank tests will be performed.

9.4.5 BASELINE DESCRIPTIVE STATISTICS

Intervention groups will be compared on baseline characteristics, including demographics and laboratory measurements, using descriptive statistics. Baseline descriptive statistics will be done for each treatment group and compared using Chi-Square Tests and t-tests as determined by variable type.

9.4.6 PLANNED INTERIM ANALYSES

Interim analysis for safety every 10 patients

9.4.7 SUB-GROUP ANALYSES

By gender

9.4.8 TABULATION OF INDIVIDUAL PARTICIPANT DATA

Cognitive measures at baseline, 6 months and 12 months

9.4.9 EXPLORATORY ANALYSES

The presence/absence of lactate will be estimated by a proportion and evaluated using a Fisher's Exact Test. The change in sizes of amygdala and hippocampus in the ipsilateral side of COICA will be using a T-Test of the difference. Improved and/or normalization of MTT and/or PTT on CTP specifically in the ipsilateral MCA territory will be analyzed using a T-Test.

10 SUPPORTING DOCUMENTATION AND OPERATIONAL CONSIDERATIONS

10.1 REGULATORY, ETHICAL, AND STUDY OVERSIGHT CONSIDERATIONS

10.1.1 INFORMED CONSENT PROCESS

Informed consent will be obtained after study details are explained in full to the patient, and the patient was provided with written informed consent to read it. The patient will be informed that the study is a research effort, that participation is fully voluntary and that refusal to participate will in no way compromise the patient's clinical care, with full disclosure of potential risks and benefits for participation.

At presentation to neurosurgery/neurology clinic, the patient will undergo neurologic, neuro-imaging evaluation, DSA, and cognitive testing as part of standard clinical care at the participating center. If the patient appears eligible on the basis of clinical and imaging (see above), the patient will be approached to obtain written consent. The consent form will contain the background of the proposed study and the benefits and risks of the procedures and will be explained in detail to the patient. Informed consent must be signed by the patient prior to enrollment. Failure to obtain a signed informed consent renders the patient ineligible for the study. Copies of the signed informed consent will be kept in the patients' file and in the medical record.

10.1.1.1 CONSENT/ASSENT AND OTHER INFORMATIONAL DOCUMENTS PROVIDED TO PARTICIPANTS

An IRB approved consent form will be utilized.

10.1.1.2 CONSENT PROCEDURES AND DOCUMENTATION

The consent form will contain the background of the proposed study and the benefits and risks of the procedures and will be explained in detail to the patient. Informed consent must be signed by the patient prior to enrollment. Failure to obtain a signed informed consent renders the patient ineligible for the study. Copies of the signed informed consent will be kept in the patients' file and in the medical record.

Unless otherwise stated, all consents are done following the strictest Good Clinical Practice (GCP) protocol. This includes proper assessment of ability to consent, time to consider enrollment with loved ones, opportunity to discuss consent with study staff, time to ask questions and receive all appropriate answers, and all other applicable components.

10.1.2 STUDY DISCONTINUATION AND CLOSURE

Participants will be informed if the study is closed prematurely or at the end of the study.

Recruitment and Enrolment will be assessed every 6 months. We anticipate enrolling 1 subject every 5 weeks and allowing for 12 months follow up visit. If the recruitment/enrolment is averaged at 1 subject per 10 weeks for 24 months, then the study will be futile and will be stopped for failure of accrual.

10.1.3 CONFIDENTIALITY AND PRIVACY

All research activities will be conducted in as private a setting as possible.

All imaging studies (MRA, CTA, and/or DSA), case report/evaluation forms, laboratory specimens, and other records will be de-identified and assigned Study Identification Number (SID) to maintain subject confidentiality. All records will be kept in a secure and locked file cabinet with keys to this cabinet only kept by the PI and/or nurse research coordinator. No clinical information will be shared or released without the written permission/consent of the patient, except as necessary for minoring by the IRB.

The study monitor, other authorized representatives of the sponsor, representatives of the Institutional Review Board (IRB), regulatory agencies or pharmaceutical company supplying study product may inspect all documents and records required to be maintained by the investigator, including but not limited to, medical records (office, clinic, or hospital) and pharmacy records for the participants in this study. The clinical study site will permit access to such records.

The study participant's contact information will be securely stored at each clinical site for internal use during the study. At the end of the study, all records will continue to be kept in a secure location for as long a period as dictated by the reviewing IRB, Institutional policies, or sponsor requirements.

Study participant research data, which is for purposes of statistical analysis and scientific reporting will be stored on secure servers. Password access for data collection and analysis will be used.

10.1.4 FUTURE USE OF STORED SPECIMENS AND DATA

Specimens will be retained for assessment of biomarkers only with permission of the participants through the informed consent.

10.1.6 SAFETY OVERSIGHT

Data and Safety Monitoring Board [DSMB]:

The DSMB will be appointed by the NIA to monitor the performance of the study. The Steering Committee will prepare regular reports summarizing patient accrual and the morbidity and mortality experienced in the study. The DSMB will also review the cumulative outcome data at regular intervals (every 6 months) or every 10 patients.

All adverse events (AEs) will be collected, recorded, and analyzed. Safety oversight for this study will be provided by both the DSMB and an independent Medical Safety Monitor ([name]).

10.1.7 CLINICAL MONITORING

The DSMB and Medical Safety Monitor ([name]) will assess the performance of the study including accrual, intervention execution, adverse events and clinical outcome assessment.

10.1.8 QUALITY ASSURANCE AND QUALITY CONTROL

Quality control (QC) procedures will be implemented beginning with the data entry system and data QC checks that will be run on the database will be generated. Any missing data or data anomalies will be communicated to the site(s) for clarification/resolution.

10.1.9 DATA HANDLING AND RECORD KEEPING

Data collection will be in compliance with ICH GCP and regulatory and UI institutional requirements for the protection of confidentiality of participants. As part of participating in a NIH-sponsored or NIH-affiliated study, the records and data will be available for authorized representatives of the NIH, sponsor, and regulatory agencies to examine (and when permitted by applicable law, to copy) clinical records for the purposes of quality assurance reviews, audits, and evaluation of the study safety, progress, and data validity. Records will be available to study staff and to IRB staff for review.

10.1.9.1 DATA COLLECTION AND MANAGEMENT RESPONSIBILITIES

Data collection will be done through case report forms created and utilized via REDCap software.

Quality control will examine range checks, missing data and incomplete data.

Data analysis for reporting and statistical analysis will be done with SAS Version 9.4.

10.1.9.2 STUDY RECORDS RETENTION

Study records will be maintained for access and review for at least 3 years after the last patient follow-up.

10.1.10 PROTOCOL DEVIATIONS

Protocol deviations must be sent to the reviewing Institutional Review Board (IRB) per their policies. The site investigator is responsible for knowing and adhering to the reviewing IRB requirements.

10.1.11 PUBLICATION AND DATA SHARING POLICY

National Institutes of Health (NIH) Public Access Policy, which ensures that the public has access to the published results of NIH funded research. It requires scientists to submit final peer-reviewed journal manuscripts that arise from NIH funds to the digital archive [PubMed Central](#) upon acceptance for publication.

This study will comply with the NIH Data Sharing Policy and Policy on the Dissemination of NIH-Funded Clinical Trial Information and the Clinical Trials Registration and Results Information Submission rule. As such, this trial will be registered at ClinicalTrials.gov, and results information from this trial will be submitted to ClinicalTrials.gov. In addition, every attempt will be made to publish results in peer-reviewed journals. Data from this study may be requested from other researchers x years after the completion of the primary endpoint by contacting <specify person or awardee institution, or name of data repository>.

In addition, this study will comply with the NIH Genomic Data Sharing Policy, which applies to all NIH-funded research that generates large-scale human or non-human genomic data, as well as the use of these data for subsequent research. Large-scale data include genome-wide association studies (GWAS), single nucleotide polymorphisms (SNP) arrays, and genome sequence, transcriptomic, epigenomic, and gene expression data.]

10.1.12 CONFLICT OF INTEREST POLICY

10.2 ABBREVIATIONS

The list below includes abbreviations utilized in this template. However, this list should be customized for each protocol (i.e., abbreviations not used should be removed and new abbreviations used should be added to this list).

AE	Adverse Event
COICA	Chronically occluded cervical ICA
MRI	Magnetic resonance imaging
CTP	CT perfusion
CTA	CT angiogram
MTT	Mean transient time
ANCOVA	Analysis of Covariance
CFR	Code of Federal Regulations
CLIA	Clinical Laboratory Improvement Amendments
CMP	Clinical Monitoring Plan
COC	Certificate of Confidentiality
CONSORT	Consolidated Standards of Reporting Trials
CRF	Case Report Form
DCC	Data Coordinating Center
DHHS	Department of Health and Human Services
DSMB	Data Safety Monitoring Board
DRE	Disease-Related Event
EC	Ethics Committee
eCRF	Electronic Case Report Forms
FDA	Food and Drug Administration
FDAAA	Food and Drug Administration Amendments Act of 2007
FFR	Federal Financial Report
GCP	Good Clinical Practice
GLP	Good Laboratory Practices
GMP	Good Manufacturing Practices
GWAS	Genome-Wide Association Studies
HIPAA	Health Insurance Portability and Accountability Act

IB	Investigator's Brochure
ICH	International Conference on Harmonisation
ICMJE	International Committee of Medical Journal Editors
IDE	Investigational Device Exemption
IND	Investigational New Drug Application
IRB	Institutional Review Board
ISM	Independent Safety Monitor
ISO	International Organization for Standardization
ITT	Intention-To-Treat
LSMEANS	Least-squares Means
MedDRA	Medical Dictionary for Regulatory Activities
MOP	Manual of Procedures
MSDS	Material Safety Data Sheet
NCT	National Clinical Trial
NIH	National Institutes of Health
NIH IC	NIH Institute or Center
OHRP	Office for Human Research Protections
PI	Principal Investigator
QA	Quality Assurance
QC	Quality Control
SAE	Serious Adverse Event
SAP	Statistical Analysis Plan
SMC	Safety Monitoring Committee
SOA	Schedule of Activities
SOC	System Organ Class
SOP	Standard Operating Procedure
UP	Unanticipated Problem
US	United States

